**A Pilot Study to assess
Spinal Cord Stimulation to Inhibit Afferent Feedback during Exercise in Hypertension**

Protocol Version: 11/27/2018

NCT02828436

Principal Investigator:

[name]., DPT, University of Minnesota

Study Summary

Title	A Pilot Study to Assess Spinal Cord Stimulation to Inhibit Afferent Feedback during Exercise in Adults with HTN
Short Title	SCS to Inhibit Afferent Feedback during Exercise
Protocol Number	1604M86961
Phase	Pilot Data
Methodology	Single blinded, randomized – order study
Study Duration	Two years
Study Center(s)	Single-center
Objectives	To investigate the exercise blood pressure response during a lower-extremity dynamic exercise in postmenopausal women with hypertension and to determine if lumbar epidural spinal cord stimulation reduces blood pressure during exercise in postmenopausal women and men with hypertension.
Number of Subjects	40
Diagnosis and Main Inclusion Criteria	Hypertension: Men and postmenopausal women between the ages of 40-90 years old. Hypertension as defined by BP \geq130/80 and diagnosed by a physician
Statistical Methodology	A two factor (condition x time) repeated measures ANOVA with sex as a between subjects factor.

List of Abbreviations

AE	adverse event
BP	blood pressure
CITI	Collaborative Institutional Training Initiative
CO	cardiac output
CT	computed tomography
CVD	cardiovascular disease
DSMB	data safety monitoring board
ECG	electrocardiogram
EPR	exercise pressor response
EXER	exercise
FSH	follicle-stimulating hormone
HIPAA	Health Insurance Portability and Accountability Act
HR	heart rate
HTN	hypertension
IRB	institutional review board
MAP	mean arterial pressure
MRI	magnetic resonance imaging
PI	principal investigator
RCO	regional circulatory occlusion
REC	recovery
RER	Respiratory Exchange Ratio
RPE	rating of perceived exertion
SAE	serious adverse event
SCS	spinal cord stimulation
SVR	Systemic Vascular Resistance
VE	ventilation
VO2	volume of oxygen uptake
VCO2	volume of carbon dioxide produced

Table of Contents

1. Introduction	5
1.1. Background and Significance.....	5
2. Specific Aims/Study Objectives.....	6
3. Investigational Device	7
4. Study Design	7
1.2. Study Design	7
1.3. Study Duration.....	8
2. Study Population	8
2.1. Inclusion Criteria.....	8
2.2. Exclusion Criteria.....	8
2.3. Recruitment	8
3. Study Visits	9
3.1. Pre-Screening	9
3.1.1. Screening and Baseline.....	10

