Despite the extensive list of major morbidity and mortality trials of antihypertensive agents (20), guidelines remain inconsistent for HTN management. Although a large variety of pharmacologic agents that, alone and in combination, are highly effective in lowering BP, ~50% of adults with HTN cannot be controlled with the drug treatment and lifestyle modification alone (1). Importantly, exercise is a treatment to lower BP and improve cardiovascular health, however with the increased risk of adverse cardiovascular or cerebrovascular events during or immediately following a bout of exercise, it limits the safety of exercise as a prescription. Further, while antihypertensive methods are similar between men and women, HTN may be less well controlled in older women (23). *There is, therefore, a critical need to determine a non-pharmacological treatment that can be used as an adjunct to exercise and lifestyle modifications for adults with HTN.*

Spinal Cord Stimulation

Modulation of afferent feedback via SCS has been used successfully for decades as a treatment for chronic pain. Each year, more than 14,000 SCS implantations are performed worldwide(22). This proposal however, seeks to test SCS as a novel non-pharmacological therapy for adults with HTN. The putative mechanism is that lumbar SCS produces vasodilation in the vasculature of the lower limbs and feet, mediated by antidromic activation of sensory fibers and decreased sympathetic outflow(22). Initial experiments to investigate the influence of SCS on BP in young healthy, demonstrated that SCS is safe and effective in young healthy adults during exercise (Figure 2). *This protocol will be the first to investigate the influence of epidural SCS on peripheral locomotor afferent feedback (group III/IV) during exercise in HTN and if there is a sex difference in the response to SCS.*

Figure 2. Spinal cord stimulation reduced mean arterial pressure (MAP) in healthy young women (A & B) (n=3), but not men (C & D) (n=5) throughout exercise and recovery (p<0.05). There was no difference between 100 Hz and 1 KHz frequencies (p>0.05). Base: resting, EXER: at the end of 2 minutes of ischemic calf-raises, RCO: regional circulatory occlusion (post-exercise), REC: 3 min of recovery

1. Specific Aims/Study Objectives

Specific Aim 1

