To investigate the EPR during a lower-extremity dynamic exercise in postmenopausal women with HTN. There is evidence to suggest that 1) premenopausal women have a blunted EPR compared with young men and postmenopausal women and 2) hormone therapy reduces the EPR in postmenopausal women. *Hypothesis:* postmenopausal women with HTN, not receiving hormone therapy, will have a greater EPR compared with men with HTN during a lower-extremity exercise.

Specific Aim 2

To determine if lumbar epidural SCS reduces BP during the EPR in postmenopausal women with HTN. Considerable evidence has accumulated over the last decade demonstrating that the EPR contributes appreciably to the abnormally augmented cardiovascular response to exercise in HTN.

Hypothesis: SCS will cause a greater reduction in the EPR in hypertensive postmenopausal women compared with hypertensive men and this attenuation will be greater with high frequency stimulation.

2. Investigational Device

The Precision Spectra system will consist of an external trial (ETS) spinal cord stimulation system, temporary percutaneous leads and lead extensions, each packaged as a separate kit. The percutaneous and surgical paddle leads function as a component of the Precision SCS system by delivering electrical stimulation to the nerve structures in the dorsal aspect of the spinal cord. Although this has typically been indicated for reductions in pain in chronic lumbar and lower leg pain patients, we will implant the leads in the same region of the lumbar spine, but will assess how spinal cord stimulation modulates blood pressure and systemic vascular resistance in adults with HTN.

Features of the Precision spectra SCS System Include:

- Stimulation electrode field navigation
- 32 independent current-controlled channels of stimulation (32 contacts + the implantable pulse generator)
- Two 16 contact Infinion leads
- High-range parameter capability
- No detectable latex

Leads

The percutaneous leads function as a component of the Precision SCS system by delivery electrical stimulation to the nerve structures in the dorsal aspect of the spinal cord, resulting in an inhibition of pain sensation.

Percutaneous Leads

The Infinion™ 16 percutaneous lead is available in lengths of 50 cm and 70 cm. Each lead has 16 contacts located near the distal end. Each contact is 3 mm in length and is spaced 1 mm from the adjacent contact.

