General Statistical Methods. Subjects will undergo submaximal exercise and ergoreceptor activation with SCS at different frequency parameters to target afferent neural feedback. Continuous variables will be presented as means \pm SD. Categorical variables will be presented as number (% population). Distribution normality will be assessed and transformations or non-parametric methods will be used as appropriate. Analyses will be conducted with SPSS (v19 or higher).

Primary Outcome Analysis. The one-minute mean BP measured at the end of the three frequency challenges will be compared using a repeated measures (on subject) ANCOVA model. The primary hypothesis will test if the pooled effect of the active frequencies (f1, f2) is significantly different from the BP with the device inactive. Post hoc comparisons of the individual frequencies will also be conducted as a part of the optimization approach. It is not known if the dose-response relationship is monotonic (i.e., higher frequency is superior in all subjects). Therefore, further analysis will be done to determine the association between the BP and frequency of SCS to reveal the dose-response curve.

Additional analysis will be conducted on an age-matched subgroup consisting of 10 postmenopausal women and 10 age-matched men.

6. Data and Safety Monitoring Plan

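### The primary comparison of end-of-challenge BP answers whether SCS lowers BP during exercise, but does not by itself test the Aim 2 hypothesis that SCS reduces the exercise pressor response (EPR)

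*Combined protocol and SAP*

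**What the plan says.** Section 5, Primary Outcome Analysis, defines the measure as a level: "The one-minute mean BP measured at the end of the three frequency challenges will be compared". The model is a "repeated measures (on subject) ANCOVA model", with no covariate named. The primary hypothesis is whether the "pooled effect of the active frequencies (f1, f2) is significantly different from the BP with the device inactive". Section 5 subtracts no resting value and does not define the EPR. Section 4 (Measures) names blood pressure as the primary outcome.

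The Study Summary gives a different model: "A two factor (condition x time) repeated measures ANOVA with sex as a between subjects factor". It does not say what the levels of time are, and section 5 does not use this model.

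Specific Aim 2 contains two statements. The objective is "To determine if lumbar epidural SCS reduces BP during the EPR in postmenopausal women with HTN". The hypothesis is that "SCS will cause a greater reduction in the EPR in hypertensive postmenopausal women compared with hypertensive men", with a larger effect at high frequency.

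On mechanism, the Spinal Cord Stimulation part of section 1.1 says that "lumbar SCS produces vasodilation in the vasculature of the lower limbs and feet", and adds reduced sympathetic outflow. On timing, the section on exercise at 30% VO2 peak with stimulation says that the device is off or on at 100 Hz or 1 kHz, in random order, during the exercise. The text describes no resting period with the stimulator already in its assigned state. Figure 4, the session timeline, is not shown in the available copy.

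**The concern.** The background treats the problem in hypertension as an exaggerated increase in BP with exercise, so the EPR is a change from rest. The primary measure is a level at one time. A level can fall because the rise is smaller or because the starting point is lower.

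Vasodilation and lower sympathetic outflow are not confined to exercise, so SCS could plausibly lower BP at rest as well. A positive primary result would then be compatible with two explanations: SCS inhibits afferent feedback during exercise (the trial's title), or SCS lowers BP generally. The pilot is meant to justify larger trials, and those would be designed differently under the two explanations.

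**Working it through.** **Inputs from the documents.** Three conditions per person (off, 100 Hz, 1 kHz); contrast of pooled active against off; 40 subjects (Study Summary, and 20 women plus 20 men per arm in section 3.1.1). The documents give no power, SD, effect size or alpha, so there is no planned figure to reproduce.

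**Assumptions, for illustration only.** Within-person residual SD of 6, 8 or 10 mmHg; a shift of 3 or 5 mmHg common to rest and exercise; two-sided 0.05; also n = 20.

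**Step 1: what the contrast contains.** For condition c, write end-challenge BP as Y(c) = R(c) + E(c), where R is rest in that condition and E is the rise. Then

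[Y(100 Hz) + Y(1 kHz)]/2 − Y(off) = ΔR + ΔE,

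where ΔR and ΔE are the active-minus-off changes in rest and rise. With ΔE = 0, the contrast equals ΔR.

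**Step 2: one baseline per session.** Subtract a single pre-session value B from all three conditions. The contrast changes by (B + B)/2 − B = 0. As a covariate, B is constant within a person and likewise leaves the within-person contrast unchanged.

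**Step 3: how often a pure shift would be significant.** SE = √(SD² × 1.5/n), df = 2n − 2, noncentral t. For n = 40 and SD 8: SE = √(64 × 1.5/40) = 1.55; noncentrality for 5 mmHg = 5/1.55 = 3.23; probability 0.89. With true ΔE = 0:

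| n | SD | 3 mmHg shift | 5 mmHg shift |
|---|---|---|---|
| 40 | 6 | 72% | 99% |
| 40 | 8 | 48% | 89% |
| 40 | 10 | 33% | 72% |
| 20 | 8 | 27% | 60% |

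**Step 4: which analysis removes the shift.** Simulation, 2,000 runs per setting, true ΔE = 0, shift −5 mmHg, SD 5 or 10, n = 20 or 40, independent rest and exercise errors:

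| Analysis | Mean contrast (mmHg) | Significant |
|---|---|---|
| Absolute end-challenge BP | about −5 | 41% to 100% |
| Minus one pre-session rest | about −5 | 41% to 100% |
| Same-condition rest as covariate | about −5 | 39% to 99% |
| Minus same-condition rest | about 0 | 5% to 6% |

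Only the rise from same-condition rest recovers the null. The rest-to-exercise condition-by-time interaction is the same quantity.

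**Step 5: the sex comparison.** The difference between women and men in the contrast is (ΔR women − ΔR men) + (ΔE women − ΔE men). A shift equal in both sexes cancels; one that differs by sex does not.

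**Step 6: cost in precision.** If rest and exercise errors have equal SD and correlation ρ, the rise has SD × √(2(1 − ρ)). At ρ = 0 the factor is 1.41. For SD 8, n = 40: SE = √(128 × 1.5/40) = 2.19; noncentrality for a true 5 mmHg effect = 2.28; power falls from 0.89 to 0.62. At n = 20 it falls from 0.60 to 0.35. Positive correlation reduces the loss; at ρ = 0.5 the factor is 1.

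**The case against.** The strongest reply is that the primary measure is right for the stated objective. The Study Summary and the Aim 2 objective both ask about BP during exercise, section 4 names BP as the outcome, and section 5 tests BP on against off. If SCS lowers BP at rest and during exercise, rejecting that null is correct, and the percentages in Step 3 are simply power to detect a real BP difference. This stands. The gap lies between the outcome and the Aim 2 hypothesis.

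A second reply is that the unnamed ANCOVA covariate or the condition-by-time model may already deal with rest. A single baseline cannot, by Step 2. Same-condition rest as a covariate did not in the simulated setting. The condition-by-time model could, but only with same-condition rest as a time level, and the plan does not say so.

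A third reply is that no resting effect has been reported. That is also correct. The legend to the pilot figure in section 1.1 reports lower MAP in young women through exercise and recovery (n=3) and claims nothing at rest. The risk is plausible, not demonstrated.

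A reader might go further and infer that resting differences between the sexes bias Aim 1. The documents do not support that: the three frequency challenges belong to the stimulation session, and section 5 states no Aim 1 analysis. A reader might also assume that continuous recording already supplies the resting data. The text describes no rest with the stimulator on, so this cannot be assumed. Nor do the documents show that a positive result would in fact be misreported as a smaller EPR.

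**Conclusion.** The concern holds in limited form. Absolute end-challenge BP is a valid primary outcome for BP during exercise, but it does not by itself test the hypothesis of a reduced EPR, because a resting effect of SCS passes into it one for one. Under the assumed values, a shift of 3 to 5 mmHg with no change in the EPR would be significant in 33% to 99% of trials with 40 participants. The shifts and SDs are assumptions, and the documents do not establish that SCS lowers resting BP. For the between-sex hypothesis, the problem arises only if the resting effect differs by sex. The algebra in Steps 1 and 2 needs none of these values. The point is worth acting on because the added analysis is inexpensive.

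**What to change.** 1. Keep absolute end-challenge BP as the primary outcome, labelled as BP during exercise.
2. Before each bout, record a one-minute resting mean with the stimulator already in that bout's assigned state (off, 100 Hz or 1 kHz). Define the EPR as the end-challenge minute minus this minute.
3. Use this rise, or equivalently the rest-to-exercise condition-by-time interaction, for the Aim 2 EPR hypothesis and its comparison between sexes. Report the resting on-versus-off difference beside it.
4. Reconcile the Study Summary model with section 5: name the ANCOVA covariate, or drop the term, and state the time levels.

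The cost is revised wording, one more analysis, and a short rest per bout if Figure 4 does not already contain one. The rise may be noisier, with a residual SD up to 1.41 times larger if errors are independent, and less if they are positively correlated. That is a further reason to add it beside the absolute measure and not in its place.

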6.1. Data

Authorized study staff and investigators who have gone through HIPAA, CITI, and other data security training through the University of Minnesota will be collecting, managing, and analyzing data. Cardiovascular variables will be monitored through use of an electrocardiogram, an intra-arterial catheter using flowtrac (Edward Life Sciences) and data from these instruments will be outputted to PowerLab (AD instruments) for offline analysis. Cardiac output and systemic vascular resistance will be measured and recorded by using the flowtrac device (Edwards Life Sciences, Irving CA). Gas exchange and ventilation variables by use of a low resistance open circuit automated metabolic system. After each study visit, subject data will be labeled by way of a random numbering system in order to anonymize the data. The data will be stored and locked in a filing cabinet. There will be a list that will link random numbering with the subject names in a computer file on a University of Minnesota computer that is secured with needing a password to access. Only study team members will be able to access this data.

In accordance with governmental regulations, study records will be kept for a minimum of three years following the completion of the study. After that time and if there is no longer a need for the records, the records will be destroyed.

6.1.1. Confidentiality

Each subject's data will be coded so that it is not identifiable to the person. The code will be secured in a locked file and on computer which will have a secure password. Blood samples will be stored in the Genomics Center in coded format.

6.2. Potential Risks

- Maximal Exercise Testing Protocol: A graded exercise protocol will be used on an upright cycle ergometer to volitional fatigue. The protocol will be discontinued immediately if any one of the following occur:

- 1) subject desire to stop,
- 2) drop in systolic blood pressure > 10 mmHg with increasing workload when accompanied with evidence of ischemia,
- 3) severe angina,
- 4) sustained ventricular tachycardia,
- 5) ST segment elevation > 1.0 mm in leads without diagnostic Q waves,
- 6) technical difficulties in monitoring ECG or systolic blood pressure or
- 7) completion of data collection.

The protocol will also be discontinued if any two of the following occur:

- 1) failure of heart rate to increase with increasing workload,
- 2) plateau in VO₂,
- 3) RER > 1.10,
- 4) perceived exertion > 18 (Borg 6-20 point scale),
- 5) systolic blood pressure > 250 mmHg, and 6) increased nervous system symptoms (e.g. ataxia, dizziness or syncope).

Risks of maximal exercise include: leg pain and fatigue, shortness of breath and general exhaustion.

- Spinal Cord Stimulator Placement: Placement of spinal leads will occur under local anesthesia (2% lidocaine). Therefore, minimal pain will be felt with electrode placement. There may be bruising or bleeding at the needle puncture site. There is a risk for infection at the insertion site which is extremely rare in healthy patients. Soreness at the needle site may occur once the local wears off. This is typically very minor and either requires no treatment or simple over-the-counter treatments. On an extremely rare occasion, nerve root/spinal cord trauma with the placement may occur that may lead to paralysis.
 - There is also a less than 1% risk of dural puncture and a "spinal headache." Spinal headaches may be present for 1-5 days and usually resolve with conservative therapy (rest, fluids, and analgesics such as ibuprofen or acetaminophen). A procedure known as a "blood patch" may be needed where the subject's own blood will be injected using similar techniques as the placement of the leads. This procedure is safe and very effective in treating spinal headaches. This risk is lower when the procedure is performed by a highly experienced individual.
 - There is no increased risk of walking with a spinal cord stimulator. Indeed, walking distance is used as a measure for patient outcomes with spinal cord stimulation(11). Less is known about exercise and SCS. In our previous study at the Mayo Clinic, however, patients were able to endure an intense ischemic exercise with SCS without adverse events (unpublished).
- Placement of arterial catheters: Risks of placing a catheter include infection or clot. These complications are extremely rare and unlikely to occur in ambulatory subjects undergoing catheterization for a few hours. A more common complication is a hematoma at the site of the

catheter placement. The physician may use ultrasound to guide the placement of the catheter, which significantly reduces this risk.

- Surface Electrodes (electrocardiography, ECG): The adhesive from the electrodes may cause slight irritation to the skin. In rare occasions, the adhesive electrodes may cause an allergic reaction.
- Magnetic Resonance Imaging: Subjects will undergo an MRI safety screening questionnaire to ensure they have no contraindications to the MRI environment. This proposal includes post-menopausal women only, however pregnancy screening will be done prior to the lumbar MRI only if menopausal status hasn't been confirmed at the time of screening.
- X-ray, CT, and Fluoroscopy: The placement of spinal leads will occur under fluoroscopy. Subjects will be exposed to low-levels of radiation. The amount of radiation that will be used has a low risk of harmful effects. The average amount of radiation that the average person would receive from fluoroscopy is approximately 1/3 (1mSv) and CT is 2 and 2/3 times (8mSv) of that received from natural sources of radiation by a Minnesota resident in one year (3 mSv).
- Sedative Use: With the use of sedatives a participant may experience dizziness, daytime drowsiness, dry mouth, change in appetite, blurred vision, diarrhea, or constipation, burning or tingling in the hands, arms or legs and unsteadiness. In rare cases of over-sedation, cardiovascular or respiratory depression may occur.
- Risks of transport from hospital to PWB CRU are minimized by: the study team, including the PI and physician transporting the participant safely between the two buildings using the service corridor which allows for both a direct route and one that is out of the general public walkway.
Details of the transport of participant are located in section 3 of protocol.

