The prevalence of HTN is higher in men until after menopause in women when the prevalence of HTN surpasses that of age-matched men(23). In the world, 25% of adult women are hypertensive, and in the United States, >75% of women over 60 years of age are hypertensive (4, 21). Aging is associated with elevated sympathetic activity. As such, sympathetic activity was found to be lower in women than in men among subjects <49 yrs., but the same in men and women among those that were ≥ 50 yrs(14). Importantly, sympathetic activity is greater in postmenopausal compared with age-matched premenopausal women(14). *In summary, the prevalence of HTN is higher in older women and sympathetically mediated increases in BP may be of more importance, demonstrating the need for investigating sex differences in the exercise blood pressure response in adults with HTN.*

Exercise Pressor Reflex in HTN

HTN can be characterized by chronic elevations in sympathetic nerve activity(13) which contributes to the abnormal augmented exercise pressor reflex(19). The afferent arm of this reflex is composed of mechanically (group III) and metabolically (group IV) sensitive skeletal muscle afferents which are known to become overactive or more sensitive in HTN (7, 15). As such, the autonomic response to exercise is altered, generating exaggerated increases in BP, heart rate, and SVR. Therefore, the risk for experiencing a cardiovascular or cerebrovascular event during or immediately after exercise is greatly elevated (6, 10, 18). This circumstance is regrettable as it limits the safety of exercise as a

treatment for HTN; a treatment with demonstrated potential for lowering BP and improving cardiovascular health (3).

[figure not shown]
Current Treatments in HTN

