2.2. Exclusion Criteria

Subjects will be excluded from participation in the study if any of the following conditions exist:

1. Unstable or uncontrolled cardiopulmonary disorders other than hypertension, as determined on the medical evaluation questionnaire.
2. History of dangerous arrhythmias (arrhythmias requiring treatment or requiring physician supervision)
3. Currently taking specific anti-hypertensive medications that may affect the exercise pressor response or influence the effect of spinal cord stimulation. We have attached a list of medications that will allow participants to be eligible for the study and medications that will exclude individuals from the study. The inclusive/exclusive exhaustive list our study team collated was done so with guidance from [name], Nephrologist.
4. History of spinal fusion or laminectomy at L3 or above
5. Current prescription opioid usage
6. At physician discretion which will be documented on the case report form.

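### In the graded maximal cycle test, nervous system symptoms alone do not require a stop, because they appear only in the any-two list (as does systolic BP > 250 mmHg)

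*Combined protocol and SAP*

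**What the plan says.** The peak oxygen uptake test is a screening procedure (section 3.1.1 and the Schedule of Assessments). Section 6.2, Potential Risks, describes it this way: "A graded exercise protocol will be used on an upright cycle ergometer to volitional fatigue". Section 4, Measures, adds that the load rises by 40 W every 3 minutes.

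Section 6.2 then gives two lists. The first opens with "The protocol will be discontinued immediately if any one of the following occur" and has seven items. The second opens with "The protocol will also be discontinued if any two of the following occur" and has six, the last two being "5) systolic blood pressure > 250 mmHg, and 6) increased nervous system symptoms (e.g. ataxia, dizziness or syncope". Neither of these two appears in the first list.

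On blood pressure, the first list contains a fall of more than 10 mmHg with signs of ischemia, and loss of the signal: "6) technical difficulties in monitoring ECG or systolic blood pressure or". It has no upper pressure limit.

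**The concern.** The second list mixes two kinds of item. Four are mainly signs that the participant has reached maximal effort: heart rate no longer rising, a plateau in oxygen uptake, RER above 1.10, and perceived exertion above 18. Asking for two of these is sensible, since any one alone is weak evidence of a maximal test. The other two, very high systolic pressure and nervous system symptoms, are safety signals. Requiring a second item before acting on a safety signal serves a different purpose, and the protocol does not explain why it is done.

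New dizziness or ataxia on an upright ergometer is the clearer case. A dizzy or ataxic participant may not ask to stop, and before maximal effort is reached there may be no effort marker to supply the second item.

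What is at stake is the safety of individual participants during the test. Section 1.1 says of adults with hypertension that "the risk for experiencing a cardiovascular or cerebrovascular event during or immediately after exercise is greatly elevated". The protocol already treats both signals as relevant to stopping; the question is only which list they belong in.

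**Working it through.** No sample size, power or error-rate figure is involved, so the check is of the rule's logic.

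**Inputs (section 6.2)**

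| List | Needed to stop | Items |
|---|---|---|
| First | any 1 of 7 | participant's wish; systolic fall > 10 mmHg with ischemia; severe angina; sustained ventricular tachycardia; ST elevation > 1.0 mm; loss of ECG or pressure monitoring; data collection complete |
| Second | any 2 of 6 | heart rate not rising; oxygen uptake plateau; RER > 1.10; perceived exertion > 18; systolic pressure > 250 mmHg; nervous system symptoms |

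**Applying the rule.** A stop is required if the first-list count is at least 1 or the second-list count is at least 2.

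| Finding | First list | Second list | Stop required? |
|---|---|---|---|
| Nervous system symptoms alone | 0 of 7 | 1 of 6 | no |
| Systolic > 250 mmHg alone | 0 of 7 | 1 of 6 | no |
| Both together | 0 of 7 | 2 of 6 | yes |
| Either, plus one effort marker | 0 of 7 | 2 of 6 | yes |
| Either, and the participant asks to stop | 1 of 7 | 1 of 6 | yes |

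**Is there another rule elsewhere?**
- Section 4 gives volitional fatigue as the endpoint and adds no safety stop.
- Section 6.3 has investigators observe for adverse events at each session, but sets no criterion for ending a test.
- Section 6.3.4 puts the study on hold after a related serious adverse event. It acts on the study, not on a test in progress.
- Section 6.4 covers reporting of emergency departures from the plan.

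None of these makes either signal a stand-alone stop.

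**Size of the gap.** After a lone signal the next 40 W step comes within at most 3 minutes. That step is reached under the written rule only if no second item appears and the participant does not ask to stop. How often this would happen cannot be worked out from the documents.

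**Effect of the fix on workload.** The stimulation section sets the session load at 30% of peak work. On that basis, one whole stage forgone lowers the load by 0.30 × 40 W = 12 W for that participant. Section 4 instead expresses the intensity as 30% of peak oxygen uptake; the 12 W figure does not apply to that definition.

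**The case against.** The strongest reply is that the lists set the minimum at which staff must stop. A reader might infer that the protocol tells staff to carry on after dizziness or a reading above 250 mmHg. It does not: nothing in section 6.2 forbids stopping on one signal, and fainting would end the cycling in any case. Nor does the rule say that the two items must be present at the same moment. If they may accumulate, the first effort marker after a signal forces a stop, and such markers are expected in a test taken to exhaustion.

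All of this stands, and it makes the gap narrow. It does not close it. Before any effort marker appears, ending the test on dizziness or ataxia alone rests on the participant's request or on individual judgement. A written list is meant to reduce that dependence.

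The second objection concerns blood pressure. A reader might infer that a single reading above 250 mmHg must be an absolute stop. The documents do not support this. Section 1.1 speaks of raised event risk but names no pressure limit, and section 6.2 uses 250 mmHg only in combination. This objection succeeds to the extent that the pressure item should be left to clinical judgement.

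A reader might also infer that the entry criteria let unsafe participants through. That is not shown. The principal investigator confirms eligibility with vital signs and medical history among the assessments (section 3.1.1), a physician may exclude at discretion (section 2.2), and the attached medication list is not available to check.

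**Conclusion.** The point holds in a limited form. As written, nervous system symptoms alone do not require the maximal test to stop unless the participant asks, and the same is true of systolic pressure above 250 mmHg. This follows directly from the two lists and needs no outside source. The case for change is stronger for nervous system symptoms; for the pressure limit it is a matter of clinical preference.

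Two of the six second-list items are affected, in a test that is part of screening. No event rate or number of harms is claimed, because the documents give none. The lists appear under the maximal test only, so nothing is concluded about the submaximal sessions.

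No bias in the trial's results is shown. The primary comparison in section 5, device off against the two active frequencies, is made within participant, so it is not confounded by how a participant's workload was set. The label is cheap improvement.

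**What to change.** 1. Move increased nervous system symptoms from the any-two list to the any-one, immediate-stop list in section 6.2.
2. Record the reason each maximal test ended, as one field on the case report form.
3. Optional, for the investigators' clinical judgement: move systolic pressure above 250 mmHg to the immediate-stop list too, keeping the protocol's own figure.
4. Leave the four remaining items under the any-two rule.

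The cost is a short amendment and one data field. A few tests may end earlier with a lower recorded peak. If session load is set from peak work, those participants would then cycle at a lower load, and their pressor response could be smaller.

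No analysis leaving these participants out is recommended. Exercise blood pressure is the primary outcome, so excluding people because their exercise pressure was very high would select on a close relative of that outcome.
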